5.2 Study Population

5.2.1 Subject Selection

Adult male and female patients will be consecutively screened for the study. Eligible patients must meet all of the inclusion criteria and none of the exclusion criteria.

The study includes 150 subjects enrolled during the primary study phase with an additional 100 subjects enrolled during the continued access phase.

5.3 Withdrawal and Lost-to-Follow-Up

Subjects may be withdrawn from the study for any of the following reasons:

- Lost-to-follow up despite exhaustive attempts to contact. A minimum of three (3) attempts to contact such subjects must be made. One such attempt must include a registered return receipt requested letter. All attempts to contact the subjects must be documented.

- Subjects may voluntarily decide to withdraw from the study. All reasonable attempts should be made to ascertain the reason for voluntary withdrawal.

All subject withdrawals must be documented on the **Study Completion/Exit Case Report Form (eCRF)**.

5.4 Duration of Study

Subject follow-up visits will occur at one, six, and 12 months post implant procedure then annually through five years. Lifelong follow-up by the physician is required after subjects have completed the study.

6.0 STUDY PROCEDURES

Treatment of subjects enrolled in this study will include tests and procedures listed in **Appendix IV: Schedule of Activities**. Placement of the AAA stent graft will be performed in accordance with the IFU.

6.1 Patient Screening

Prospective candidates are evaluated in a consecutive manner for eligibility for the study at the time they are considered to be candidates for AAA repair. Initial screening may include diagnostic testing (e.g., imaging, angiogram, laboratory testing) performed as part of routine medical care.

The following steps outline the process to determine patient eligibility for enrollment and subsequent shipment of the device(s):

1. Ensure that patient has signed an IRB approved Informed Consent Form, per Institutional policies
2. Complete the Eligibility Verification Worksheet form
3. Complete the AAA Pre-Operative Sizing Worksheet
4. Fax #2 and #3 (above) to TriVascular Clinical Department [contact])
5. Submit contrasted spiral CT images to Core Lab obtained within 6 months of anticipated treatment.

Refer to Manual of Operations for Core Lab Imaging Guidelines.

6.2 Pre-procedure evaluation

The following assessments will be performed no more than one month prior to the implant/surgical procedure:

- Patient demographics
- Medical/surgical history
- Physical exam
- Ankle-Brachial Index (ABI) measurement
- Laboratory testing, which includes renal and coagulation assessment, as well as serum pregnancy for female patients of childbearing potential.

If the patient is eligible to be enrolled into the study, the results of these screening assessments are recorded on the **Baseline eCRF**. If a patient does not qualify for enrollment into the study, the baseline screening worksheets will be retained, together with the patient's signed/dated consent(s).

6.3 Treatment period (implant/surgical procedure)

The following assessments and data collection will be performed at the time of the implant/surgical procedure:

- Investigational device accountability- documentation of product information (e.g., lot number, serial number, and expiration date).
- Type and length of anesthesia
- Anticoagulation
- Description of delivery system access on both ipsilateral and contralateral sides (e.g. femoral cut down, percutaneous access, closure device)

- Type and volume of contrast used
- Total fluoroscopy time during procedure
- Estimated blood loss and replacement requirements
- Adjunctive procedures (e.g. stent placement)
- Investigator assessment of AAA device performance as it relates to:
 - Access success/failure, delivery/deployment success, evidence of endoleak, device integrity issues
- Procedural times (time of initial arterial access, stent graft deployment start and stop time, polymer mix completion time, delivery system removal time, and time of closure of arterial access)
- Adverse events

6.4 Pre-Discharge

The following assessments and testing will be performed post-procedure, prior to discharge:

- Physical exam
- Ankle-Brachial Index (ABI) measurement
- Laboratory testing, which includes renal and optional coagulation assessment
- Length of hospital stay
- Abdominal X-ray (KUB), including AP, lateral, left oblique and right oblique views. This X-ray will serve as the baseline for all future evaluations of device integrity and can be performed within 7 days following hospital discharge.
- Concomitant medications (anticoagulants, antiplatelets and antibiotics only)
- Adverse events
- Other relevant data as indicated on the CRF, including optional wound assessment.

The above assessments are recorded in the **Hospital Discharge eCRF**. In some instances, subjects may experience a prolonged hospitalization post procedure. In those cases, the above assessments should be performed no more than two (2) weeks post procedure.

6.5 Post-Treatment follow-up period

The following assessments and tests will be performed at the following intervals:

Time period post-treatment	Acceptable visit timeframe allowance
1 Month (30 days)	± 14 days
6 Months (180 days)	± 30 days
12 Months (365 days)	± 60 days
Annually from 2 to 5 years	± 60 days

- Physical exam
- Laboratory testing, which includes renal and optional coagulation assessment
- Contrast Enhanced Spiral Abdominal/Pelvic CT
- Abdominal X-ray (KUB), including AP, lateral, left oblique and right oblique views Device/aneurysm assessment based on imaging (endoleak, migration, integrity, patency, AAA dimensions)
- Concomitant medications (anticoagulants, antiplatelets and antibiotics only)
- Adverse events
- Other relevant data as indicated on the CRF including optional wound assessment.

The above assessments are recorded in the appropriate **Follow-up Visit eCRF**. Note that in the event the subject is unable to tolerate a contrast-enhanced spiral CT, a duplex ultrasound and non-contrast spiral CT should be completed as an alternative assessment.

6.6 Unscheduled Follow-up visits

In the event that a subject visit occurs outside the protocol-specified time frames (i.e., Pre-discharge, 1 month, 6 month, 12 month) sites are required to record data from that visit, if that visit is specifically associated with the device, procedure or aneurysmal disease. Possible reasons for unscheduled visit data collection may be:

- Subject experiences new symptomatology and/or an adverse event
- Surveillance of an existing adverse event

The Unscheduled visit information would be recorded in the **Follow-up Visit eCRF where the reason for the unscheduled visit will be specified**.

If a subject is seen in the office or clinic for other reasons than listed above, information from that visit would be recorded on the next protocol-specified visit in the appropriate **Follow-Up CRF**.

6.7 Annual follow-up visits

Subjects who have completed 12 months of follow-up will continue annual follow-up exams (+/- 2 months) for 5 years.

The following assessments and tests will be performed at annual visits through 5 years:

- Physical exam
- Laboratory testing, which includes renal and optional coagulation assessment
- Contrast Enhanced Spiral Abdominal/Pelvic CT
- Abdominal X-ray (KUB), including AP, lateral, left oblique and right oblique views
- Device/aneurysm assessment based on imaging (endoleak, migration, integrity, patency, AAA dimensions)
- Concomitant medications (anticoagulants, antiplatelets and antibiotics only)
- Adverse events
- Other relevant data as indicated on the CRF, including optional wound assessment.

6.8 Discontinuation from study

Subjects who choose to discontinue participation in the study prior to study completion will be requested to undergo a final assessment by the investigator at the time notification is made of their decision to discontinue. If the subject notifies the clinical site of discontinuation by mail or phone, subject will be requested to have a final assessment by the investigator.

The final assessment will be recorded in the **Follow-up Visit and Study Completion/Exit eCRFs**.

7.0 STUDY OBJECTIVES

The purpose of this pivotal clinical trial is to evaluate the safety and effectiveness of the Ovation Abdominal Stent Graft in the treatment of subjects with abdominal aortic aneurysms (AAA).

7.1 Primary Objectives

The primary objective of this study is to determine whether the Ovation Abdominal Stent Graft System is a safe and effective method of treating AAAs in those subjects considered to be suitable candidates for open surgical repair.

The safety of the Ovation Abdominal Stent Graft System will be determined by proportion of subjects with major adverse events.

The effectiveness of the Ovation Abdominal Stent Graft System will be determined by the proportion of subjects that achieve treatment success.

8.0 DEFINITIONS

8.1 Endoleak

Endoleak is defined by the persistence of blood flow outside the lumen of the endovascular graft but within the aneurysm sac and can be classified as:

Type I – Ineffective seal at either the proximal or distal sealing zones

Type II – Retrograde blood flow from lumbar arteries, the inferior mesenteric artery, or other collateral vessels into the aneurysm sac

Type III – A leak caused by fabric tears or disruption, component disconnection, or graft disintegration

Type IV – Blood flow through an intact fabric.

8.2 Migration

Migration is defined as evidence of proximal or distal movement of the stent graft >10mm relative to fixed anatomic landmarks. Spiral CT images will be used to determine migration at regularly scheduled follow-up visits. The 1 month image will be used as the baseline assessment.

8.3 Patency

Patency is defined as the absence of complete occlusion of the treated vessel. This may be evidenced by: CT, angiography, ultrasound or other imaging modality, or pathological analysis.

8.4 Loss of Stent Graft Integrity

The integrity of the stent graft will be evaluated by abdominal x-rays at regularly scheduled follow-up visits. Any fractured stents, and any other issues compromising the integrity of the stent graft will be reported.

8.5 AAA Enlargement

Aneurysm enlargement is defined as a greater than 5 mm (diameter) increase in the aneurysm size. Spiral CT images will be used to determine aneurysm enlargement at regularly scheduled follow-up visits. The 1 month image will be used as the baseline assessment. In addition, aneurysm volume will be assessed by the Core Lab and reported in the data analysis, but diameter is considered the relevant characteristic for the study endpoint evaluations.

8.6 Surgical Conversion

Surgical conversion occurs when a subject implanted with an Ovation Abdominal Stent Graft undergoes open surgical repair with explantation of the stent graft. The follow-up for subjects who are converted to open surgical repair include collection of the following data: Physical Exam and assessment of Adverse Events. The visits are to occur at 1 month post open conversion and 1 year post open conversion.

8.7 Imaging Core Lab

TriVascular will utilize an independent imaging Core Lab to analyze device performance specifically related to study endpoints such as: device integrity, endoleaks, migration, and aneurysm dimensions (e.g., length, diameter, volume). Clinical sites will submit all CT and X-ray images to the Core Lab for all required study visits.

Study Visit	Images* Required to be submitted to Core lab
Baseline (pre-op)	Contrast Enhanced Spiral Abdominal/Pelvic CT
Discharge (post-op)	Abdominal X-rays (AP, lateral, left oblique and right oblique views)
1 month (16 - 44 days)	Abdominal X-rays (AP, lateral, left oblique and right oblique views) Contrast Enhanced Spiral Abdominal/Pelvic CT
6 month (150 - 210 days)	Abdominal X-rays (AP, lateral, left oblique and right oblique views) Contrast Enhanced Spiral Abdominal/Pelvic CT
12 month (305 - 425 days)	Abdominal X-rays (AP, lateral, left oblique and right oblique views) Contrast Enhanced Spiral Abdominal/Pelvic CT

*Refer to **Appendix VI: CT Scanning Techniques** and Manual of Operations for Core Lab imaging requirements.

8.8 Explant Evaluation

TriVascular is committed to understanding the effects of the human *in vivo* environment on the stent graft over time. To this end, all explanted devices should be returned to TriVascular for evaluation by a Pathologist at an independent Explant Laboratory. Refer to **Appendix VII: Explant Procedure** and the Manual of Operations for specific instructions for managing the removal, shipping, and handling of the explanted AAA device.

8.9 Adverse Events

An adverse event is any new, undesirable medical occurrence or change (worsening) of a pre-existing condition that occurs in a subject, whether or not considered to be associated with the product. Elective hospitalizations for pre-existing conditions (e.g., elective cosmetic procedures) are not adverse events.

Requirements for reporting AEs are dependent upon the reviewing IRB policy. Adverse events will be reviewed by a Clinical Events Committee (CEC). The CEC will meet periodically, a minimum of annually.

Adverse Event information is recorded in the **Adverse Event eCRF**.

For purposes of this study, the following events are not considered adverse events, because they are expected to occur in conjunction with the index procedure or are associated with customary, standard care of subjects undergoing endovascular AAA repair procedures:

- Early post-operative pain (within 24 hours of index procedure) at the access site and/or related to position on procedure table

- Post-anesthesia/conscious sedation emesis, nausea, or headache (within 24 hours of index procedure)
- Electrolyte imbalance without clinical sequelae following index procedure, even if requiring correction
- Low grade temperature increase (< 101.0 °F)
- Hematocrit decrease from baseline of less than 6 points (2 grams of hemoglobin) that remains above 30% and is not associated with hemodynamic changes and does not require transfusion
- Blood loss not requiring transfusion and not resulting in decreased hematocrit.
- Minor, localized tenderness, swelling, induration, bruising, erythema, hematoma etc. at vascular access site that does not require surgical intervention, evacuation, transfusion, or antibiotics
- Prophylactic administration of atropine
- Prophylactic pacing
- Isolated, non-sustained PVCs/PACs
- Non-sustained, arrhythmia not requiring treatment or intervention
- Hypotension or hypertension not requiring treatment or intervention
- Atelectasis not requiring treatment

The Investigator and/or IRB may require that these events are reported as adverse events. In this case, the Investigator should report these observations based on their medical judgment and requirements of the IRB.

Device-related adverse events should be reported to the sponsor within 24 hours of knowledge of the event.

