8.11 Major Adverse Events (MAE)

The following specific events will be considered major adverse events (MAE) for the purpose of evaluating the primary (30 day) and secondary (1 year) safety endpoints:

Major adverse events (MAE) are defined as any one of the following events:

- Death
- Myocardial Infarction
- Stroke (excludes TIA)
- Renal Failure (excludes renal insufficiency)
- Respiratory Failure (excludes COPD or pulmonary complications)
- Paralysis (excludes paraparesis)
- Bowel Ischemia
- Procedural Blood Loss ($\geq 1,000$ cc)

A major adverse event (MAE) may or may not be considered related to the device. Mortality will be reported as "all cause" and "AAA related." All deaths occurring in the first 30 days post-index procedure are considered "AAA related."

The Clinical Events Committee (CEC) shall determine which adverse events are considered Major Adverse Events (MAE) for evaluation of the primary (30 days) and secondary (1 year) safety endpoints.

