9.1 Primary Endpoints

9.1.1 Safety

The primary safety endpoint is the rate of major adverse events (MAE) at 30 days post procedure. The following specific events will be considered major adverse events:

Major adverse events (MAE) are defined as any one of the following events:

- Death
- Myocardial Infarction
- Stroke (excludes TIA)
- Renal Failure (excludes renal insufficiency)
- Respiratory Failure (excludes COPD or pulmonary complications)
- Paralysis (excludes paraparesis)
- Bowel Ischemia
- Procedural Blood Loss ($\geq 1,000$ cc)

A major adverse event (MAE) may or may not be considered related to the device. Mortality will be reported as “all cause” and “AAA related.” All deaths occurring in the first 30 days post-index procedure are considered “AAA related.”

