10.0 STATISTICAL CONSIDERATIONS

10.1 Primary Endpoints and Hypotheses

10.1.1 Primary Safety Endpoint and Hypothesis: Major Adverse Event Rates

This study is designed to compare the rate of major adverse events following abdominal aortic aneurysm repair with the Ovation Abdominal Stent Graft System to a target performance goal. The proportion of subjects receiving the Ovation Abdominal Stent Graft who experience one or more events meeting the definition of a major adverse event within 30 days of the initial procedure is the rate of interest. The null and alternative hypotheses are given below:

$$H_0: \pi_T \geq 21\%$$

$$H_1: \pi_T < 21\%, \text{ where}$$

π_T is the expected proportion of subjects undergoing AAA repair with the Ovation Abdominal Stent Graft System who experience a major adverse event at 30 days. The target performance goal rate of 21% is that based on the 11% rate (plus 10% "non-inferiority" margin) of major adverse events at 30 days reported for the Medtronic Talent device (reported in the Medtronic Talent Summary of Safety and Effectiveness Data 2008).

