13.2 Clinical Events Committee

The Clinical Events Committee (CEC) shall be used to review and adjudicate all device related adverse events (AE) and all serious adverse events (SAE) regardless of the relatedness to the device. The CEC shall also determine which adverse events are considered Major Adverse Events (MAE) for evaluation of the primary (30 days) and secondary (1 year) safety endpoints. The committee shall consist of at least three (3) physicians representing multiple specialties familiar with abdominal aortic aneurysm repair. The CEC will provide their review to the DSMB and shall meet annually, at a minimum.

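### Does the adverse-event exclusion for some blood loss in Section 8.9 remove a procedural loss of 1,000 cc or more from the primary safety endpoint?

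*Combined protocol and SAP*

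**What the plan says.** Section 8.9 defines an adverse event broadly and then sets some findings aside. It says "the following events are not considered adverse events, because they are expected to occur in conjunction with the index procedure", or because they belong to usual care after endovascular repair. One entry reads "Blood loss not requiring transfusion and not resulting in decreased hematocrit". The list names no volume and makes no exception for MAE components. It ends by leaving room to report: "The Investigator and/or IRB may require that these events are reported as adverse events".

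Section 8.11 introduces its components with the words "The following specific events will be considered major adverse events (MAE) for the purpose of evaluating the primary (30 day", and extends them to the one-year secondary endpoint. The last of the eight components, there and again in Section 9.1.1, is "Procedural Blood Loss" of 1,000 cc or more. Section 8.11 also says that the CEC "shall determine which adverse events are considered Major Adverse Events (MAE) for evaluation of the primary (30 days) and secondary (1 year) safety endpoints", and Section 13.2 repeats this.

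The analysis rule is in Section 10.1.1. The rate of interest is the proportion of Ovation subjects "who experience one or more events meeting the definition of a major adverse event within 30 days of the initial procedure". Section 6.3 has estimated blood loss recorded at the procedure. Sections 9.2.3 and 10.4.2 make it a secondary measure, analysed for each subject.

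**The concern.** Read in sequence, the text seems to close a route. Section 8.9 says that a certain blood loss is not an adverse event, whatever its volume. The CEC picks MAEs from among adverse events. A loss of 1,000 cc or more that needed no transfusion and left the hematocrit unchanged would then never reach the committee, although Sections 8.11 and 9.1.1 call it an MAE. No sentence says which section prevails.

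The direction would matter. An uncounted event can only lower the MAE rate, and this is a single-arm study judged against a fixed goal of 21%, so any loss would favour the device.

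**Working it through.** **Step 1: the passages side by side.**

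| Section | What it governs | Conditions on blood loss |
|---|---|---|
| 8.9 | General adverse event reporting | No transfusion and no fall in hematocrit; no volume |
| 8.11, 9.1.1 | Definition of the primary safety endpoint | Volume of at least 1,000 cc; nothing else |
| 10.1.1 | What the analysis counts | The event meets the MAE definition |

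Section 8.9 is a general reporting rule. Sections 8.11 and 9.1.1 are written for the endpoint and state without qualification that the listed events are MAEs. Section 10.1.1 ties the count to that definition, not to whether an adverse event form was filed. The specific rule therefore controls the endpoint.

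The reason given in Section 8.9 points the same way. Its list covers what is expected with the procedure or is customary care. A loss that the same protocol names as a major adverse event does not fit that description.

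**Step 2: the size of the overlap.** The Section 8.9 entry requires both conditions together. A subject falls in both rules only with a loss of at least 1,000 cc, no transfusion and no decrease in hematocrit. Any decrease takes the loss outside the entry. The neighbouring entry on small hematocrit falls excludes the hematocrit change, not the blood loss, so it does not clearly widen the overlap. The documents give no frequency for this combination and no sign that it would occur.

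**Step 3: whether the data exist.** Estimated blood loss is recorded at the procedure (6.3) whether or not an adverse event is reported, and it is an outcome for each subject (10.4.2). A loss above the threshold would be visible in the database.

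**Step 4: scale, as an illustration.** Inputs: n = 150 and an assumed rate of 11% (10.2); goal 21% (10.1.1); one-sided 5% level and Formula 1 with Z = 1.645 (10.3.1).

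The plan's stated power is 96%. By the normal approximation with the null variance:

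Power = Φ[(0.10·√150 − 1.645·√(0.21·0.79)) / √(0.11·0.89)] = Φ[(1.2247 − 0.6700)/0.3129] = Φ(1.773) = 96.2%.

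The stated figure reproduces, and the blood-loss question does not touch it.

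Formula 1 with x events, where np = x and Z² = 2.706:

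- x = 23 (15.3%): U = (48.706 + 1.645·√80.599)/305.412 = 20.8%, pass.
- x = 24 (16.0%): U = (50.706 + 1.645·√83.346)/305.412 = 21.5%, fail.

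One uncounted subject changes the result only if the true count is exactly 24. Exact binomial, n = 150:

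| True MAE rate | Pass, none uncounted: P(X ≤ 23) | Pass, one uncounted: P(X ≤ 24) | P(X = 24) |
|---|---|---|---|
| 11% | 96.10% | 97.70% | 1.61% |
| 16% | 46.57% | 55.42% | 8.85% |
| 21% | 5.06% | 7.71% | 2.65% |

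These figures suppose that one subject's only MAE is such a loss and that it goes uncounted. They are not a bound: with two such subjects, the chance of passing at a true rate of 16% would go from 46.6% to 63.9%. The documents give no probability for either case.

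**The case for a change.** The strongest case separates definition from ascertainment. Even if the definition is clear, the described route to an MAE runs through adverse events. Section 13.2 has the CEC review device-related adverse events and all serious adverse events, and the Section 8.9 let-out is discretionary. No sentence sends the recorded volume to the committee or derives the component from it. In addition, the laboratory panel in Appendix IV is BUN, creatinine, PT, PTT and INR. Hematocrit is not scheduled, so a site could apply the exclusion without a protocol-required value to support it.

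Part of this stands. There is no precedence sentence, and the hematocrit point is correct. But neither shows that the plan, followed as written, miscounts. No MAE component has a stated source field or derivation; blood loss is the one with a numeric threshold and a value recorded for it, so it is the easiest to verify. Section 10.9 leaves the detailed description of the analysis to a plan written before database lock, where such a derivation would normally sit. The missing hematocrit test also cuts both ways: without a value, a site cannot show that the exclusion applies. A rule that counted the recorded volume automatically would itself have to be squared with the CEC's role under Sections 8.11 and 13.2.

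**Conclusion.** The concern does not hold. Procedural blood loss of 1,000 cc or more is an MAE under Sections 8.11 and 9.1.1, and Section 10.1.1 counts it. The general list in Section 8.9 does not narrow the endpoint. What remains is a wish for a sentence confirming precedence, which is a matter of drafting detail. N, alpha, power and the decision rule are unaffected.

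This conclusion rests on reading the endpoint-specific definition as controlling, which is the natural reading, and on the volume being recorded at each procedure as Section 6.3 requires. It does not rest on any assumed frequency of the overlap, because the documents give none. The table above illustrates one subject and does not estimate a bias.
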